#### **Main Eligibility**

#### **Criteria**

#### Inclusion Criteria

- Adult females between the ages of 35-75, seeking treatments for pelvic floor relaxation syndrome or atrophic vaginitis, which include but are not limited to: pelvic floor laxity, decreased muscle contraction in the pelvic floor, urinary incontinence, sexual dysfunction.
- Participants must have an evaluation by the Pelvic Floor Physical Therapists at Antares Institute. All participants must have a minimum of 30% below average reading on initial assessment of internal or external pelvic floor contraction in order to be included in the study.
- Negative PAP smear and pelvic exam done within last 1 year.
- The patients should understand the information provided about the investigative nature of the treatment, possible benefits and side effects, and sign the Informed Consent Form, (including the permission to use photography).
- The patients should be willing to comply with the study procedure and schedule, including the follow up visit, and will refrain from using any other treatment methods in the treatment areas such surgeries, CO2 treatment, other radiofrequency treatments and fillers injections for the last 12 months and during the entire study period.
- [name] will be available for consultation as needed throughout the course of the study. He will also review all documentation as needed.

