**Study Objectives****Primary Objective:**

Evaluate the effects of radiofrequency on pelvic floor strength as measured by intentional muscle contraction.

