**Objective measurements:**

- Genitalia(vaginal and labia) condition and intentional muscle contraction will be evaluated at baseline, before each treatment and at follow up visits (8 weeks after each treatment). Visits 2, 4 and 6.

- Physical measurements of vagina, vulvar and perineal areas will be measured according to POP-Q guidelines. (Appendix 11.0) Visits 2, 4 and 6.

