**Study Duration**

Study duration for each subject is approximately four months (including screening, 2 treatment sessions 8 weeks apart and a follow-up visit at 8 weeks post last treatment.

Overall study duration will be approximately 12 months, depending on the subject recruitment rate.

Each subject will undergo 7 study visits including screening, 2 treatment and 1 follow-up visit.

**Visit 1:** Midwest Plastic Surgery-Evaluation

- Screening will be performed to determine subject eligibility as well as to collect all of the required medical information and obtain signed Informed Consent.
- Baseline photographs of the treatment area will be taken
- Pre-procedure questionnaires will be completed at this time
- Time required 1.5 hours

**Visit 2:** Antares Institute-Evaluation

- A complete pelvic floor assessment will be performed including but not limited to the following: measurement of internal and external pelvic floor contraction, measurement of vaginal canal length and diameter, measurement of the introitus, and length of the labia majora and minora. Measurements will be obtained following POP-Q protocol
- This visit will confirm inclusion criteria based on measurements.
- Time required: 1.5hrs

**Visit 3:** Midwest Plastic Surgery – 1st treatment

- Internal and external FormaV treatment
- Photographs of the treatment area will be taken after the procedure.
- Time required: 45 minutes

**Visit 4:** Antares Institute Follow-up visit – 8 weeks following first treatment

- A complete pelvic floor assessment will be performed including but not limited to the following: measurement of internal and external pelvic floor contraction, measurement of vaginal canal length and diameter, measurement of the introitus, and length of the labia majora and minora. Measurements will be obtained following POP-Q protocol.
- Time required: 15 minutes

**Visit 5:** Midwest Plastic Surgery – 2nd treatment

- Photographs of the treatment area will be taken before and after the procedure.
- Questionnaires will be completed.
- Time required: 45 minutes

**Visit 6:** Antares Institute Follow-up visit – 8 weeks following second treatment

- A complete pelvic floor assessment will be performed including but not limited to the following: measurement of internal and external pelvic floor contraction, measurement of vaginal canal

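### One institute takes the qualifying, baseline and follow-up contraction readings, and with no control arm and no masking described, the primary-objective measure is open to assessor bias

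*Protocol*

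**What the plan says.** The primary objective (Protocol, Study Objectives) concerns "pelvic floor strength as measured by intentional muscle contraction". Three parts of the plan bear on who takes that reading and when.

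- **Entry (Protocol, Inclusion Criteria).** "Participants must have an evaluation by the Pelvic Floor Physical Therapists at Antares Institute", and "All participants must have a minimum of 30% below average reading on initial assessment of internal or external pelvic floor contraction".
- **Baseline (Protocol, Study Duration, Visit 2).** The pelvic floor assessment takes place at the same institute, and "This visit will confirm inclusion criteria based on measurements". Under Objective measurements, Visit 2 is also the only pre-treatment visit among those listed for contraction (Visits 2, 4 and 6). The entry reading and the baseline are thus the same reading.
- **Follow-up (Protocol, Study Duration).** Visit 4 is headed "Antares Institute Follow-up visit – 8 weeks following first treatment" and Visit 6 "Antares Institute Follow-up visit – 8 weeks following second treatment". Both repeat the Visit 2 assessment. Treatment is given at another site, at Visits 3 and 5.

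The SAP (section I.B) compares scores before treatment with scores at follow-up by a paired t-test at a two-sided 0.05 level. The Protocol describes the design only as prospective. Neither document mentions a control arm, masking, an independent assessor, withholding of earlier readings, or a standard instruction to the woman.

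**The concern.** A voluntary contraction depends at least partly on the woman's effort, and so potentially on how she is prompted. The plan does not name the instrument behind the contraction reading or say how she is to be instructed. An assessor who can see a low Visit 2 value, and knows that the woman has since been treated, may prompt or read differently at Visit 4 or 6 without meaning to.

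In a controlled trial with assessors masked to treatment, such a shift would affect both arms and largely cancel. Here nothing subtracts it: the mean change estimates the device effect plus any assessor shift plus everything else that changes over time. At stake is whether a significant change in contraction can be credited to the device.

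**Working it through.** **The plan's own figure.** The Protocol asks for at least 20 women and gives no effect size, SD, power or dropout rate. The sample size therefore cannot be reproduced. It serves below only as *n*.

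**Inputs**
- *n* = 20, df = 19 (Protocol, Patient Population and Sample Size).
- Paired t-test, two-sided 0.05 (SAP I.B).
- True device effect: zero (assumed, to isolate the bias).
- *b* = mean assessor-driven shift, in units of the SD of the change score. The documents give no SD or measurement error, so every value of *b* is an assumption.

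**Step 1: the smallest significant change.** The critical value is t(0.975, 19) = 2.093. A mean change is significant once it exceeds 2.093 / √20 = 2.093 / 4.472 = 0.468 SD of the change.

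**Step 2: chance of a significant improvement when only bias is present.** The test statistic follows a noncentral t with df 19 and noncentrality *b*√20. The upper-tail chance is 1 − F(2.093; 19, *b*√20). The lower-tail chance is F(−2.093; 19, *b*√20).

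| *b* (assumed) | *b*√20 | Significant improvement | Either direction |
|---|---|---|---|
| 0 | 0 | 0.0250 | 0.0500 |
| 0.1 | 0.447 | 0.0624 | 0.0709 |
| 0.2 | 0.894 | 0.1335 | 0.1360 |
| 0.3 | 1.342 | 0.2465 | 0.2471 |

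**Step 3: the opposite direction.** If the assessor instead anchors on the low baseline value, *b* is negative. By symmetry, the chance of a significant improvement is then the lower tail of the matching positive row. At *b* = −0.2 that is 0.1360 − 0.1335 = 0.0025, against 0.0250 with no bias. A real benefit would be partly hidden.

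**Step 4: can earlier values be withheld within this schedule?** Eligibility is settled once Visit 2 is complete, and treatment is given at a different site. Nothing in the visit schedule requires the assessor at Visit 4 or 6 to see an earlier reading.

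**The case against.** The strongest case against runs as follows.

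- **The same therapists.** A reader might infer that the individuals who qualify each woman also re-measure her. The documents do not show this. The Inclusion Criteria assign the qualifying evaluation to the institute's therapists as a group, and the text for Visits 4 and 6 gives only the site. This limits the claim but does not remove it, since any assessor there with access to the record could see the earlier value.
- **Values on view.** A reader might also infer that earlier readings are shown at follow-up. The plan is silent. Silence leaves access uncontrolled, but does not establish it.
- **The primary endpoint.** Contraction is the measure in the primary objective. The items under Primary Endpoints are visit completion and voluntary withdrawal, so it would be wrong to say that the listed primary endpoint is biased. That mismatch is a separate matter.
- **Method unknown.** The contraction method is not named, and the Protocol classes the reading as an objective measurement. How far an examiner can influence it is therefore not known. This stands.
- **Masking is weak here.** Every woman enters with a low reading and every woman is treated, so the assessor knows both facts whatever the form shows. A therapist who took the Visit 2 reading may also remember it. This stands, and it limits what the fix can achieve.
- **Larger problems exist.** Reusing the qualifying low reading as the baseline produces regression to the mean even with a perfectly neutral assessor. That is true, and this fix does not touch it. It is no reason to leave a nearly free safeguard out.

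**Conclusion.** The point holds as a cheap improvement. The documents establish three things: one institute takes the qualifying, baseline and both follow-up readings; no masking is described; and there is no control arm. An assessor-driven shift of any size would enter the paired comparison undiminished.

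Its size and direction are unknown. On assumed upward shifts of 0.1, 0.2 and 0.3 SD of the change, with 20 women and no device effect, the chance of a significant improvement rises from 2.5% to about 6%, 13% and 25%. A downward shift would lower that chance and could hide a real effect.

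A reader might take these percentages as evidence that the trial is biased towards the device, or as the gain from the fix. They are neither. They show only that a modest shift would matter at this sample size, and masking would remove an unknown part of any such shift.

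**What to change.** Add a few sentences to the Protocol under Objective measurements and under Study Duration (Visits 2, 4 and 6):

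1. Use the same fixed instruction script and the same measurement procedure at Visits 2, 4 and 6. The script must be in use at Visit 2 as well; introduced only at follow-up, it would itself create a difference from baseline.
2. Record Visit 4 and Visit 6 values on blank forms.
3. File each completed form so that earlier values are not available to the assessor at the next visit.
4. Where existing staffing allows, have a therapist other than the Visit 2 assessor take the follow-up readings.

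**Cost.** One form per visit, a short script and the added text. No extra visit, procedure or staff is needed, since the fourth step applies only where a second therapist is already available. Therapists lose the ability to refer back to earlier readings. Changing therapist can add between-examiner differences. The common procedure limits these, and so does avoiding an arrangement in which one therapist takes all the baselines and another all the follow-ups.

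The Protocol should state that masking is partial. Regression to the mean needs its own remedy.

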**Patient Population and Sample Size**

At least 20 female subjects ages 35-75 selected based on evaluation of symptoms including the following: urinary incontinence, pelvic floor laxity.

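### The Visit 2 contraction reading both selects women for low values and serves as their baseline, so with no control arm regression to the mean biases the contraction change towards a gain

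*Protocol*

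**What the plan says.** The primary objective in the Protocol is: "Evaluate the effects of radiofrequency on pelvic floor strength as measured by intentional muscle contraction". Entry depends on the same measure. Under Inclusion Criteria, "All participants must have a minimum of 30% below average reading on initial assessment of internal or external pelvic floor contraction". The rule is applied at Visit 2, the first visit with a pelvic floor assessment. Of that visit the Study Duration section says: "This visit will confirm inclusion criteria based on measurements".

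Under Objective measurements, contraction "will be evaluated at baseline, before each treatment and at follow up visits (8 weeks after each treatment). Visits 2, 4 and 6". Visit 4 falls 8 weeks after the first treatment and Visit 6 falls 8 weeks after the second. Visit 1 lists questionnaires and photographs. Visit 3 lists "Internal and external FormaV treatment" and photographs, with no contraction reading.

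No comparison group is described: "Each subject will undergo 7 study visits including screening, 2 treatment and 1 follow-up visit". Section I.B of the SAP plans a paired t-test of before-treatment against follow-up scores at two-sided 0.05. It has no repeat baseline and no adjustment for selection. The Protocol's Efficacy Endpoints section presents the comparison with baseline as measuring what Forma V does.

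**The concern.** A reading is the woman's usual level plus error. Women who pass a low cut-off have, on average, an error at Visit 2 that pulled the reading down. Errors at Visits 4 and 6 are not selected in this way, so the average reading rises with no treatment effect at all. With no control arm, nothing in the data separates this rise from a benefit.

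What is at stake is the primary objective. A significant paired t-test on contraction would be read as an effect of radiofrequency when some or all of it may come from the entry rule. Recruiting more women does not shrink the bias. It makes the biased difference easier to declare significant, and 20 is only a minimum ("At least 20 female subjects ages 35-75 selected based on evaluation of symptoms"). The questionnaires are not affected by this mechanism, because they have no entry cut-off and their own baseline at Visit 1.

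**Working it through.** **From the documents.** Cut-off at least 30% below average on the internal or the external reading; the same Visit 2 reading as baseline; paired t-test, two-sided 0.05; at least 20 women. The plan has no figure to reproduce here: 20 comes without an SD, effect size or power, and the reference average is not given.

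**Assumed, not in the documents.** Average 100, so cut-off *c* = 70; normal readings with the same mean μ and SD in both channels; SD 30 to 40; reliability *R* 0.7 to 0.9; correlation 0.5 between the true internal and external levels; error correlation *r* between the channels at one visit; follow-up errors independent of Visit 2 errors; one channel tested; no treatment effect.

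**Step 1: selection on the tested reading alone.** Expected null change = SD × (1 − R) × φ(a)/Φ(a), with a = (c − μ)/SD. For μ = 85, SD = 30, R = 0.7: a = −0.5, and 30 × 0.3 × 0.3521/0.3085 = 10.3 points.

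**Step 2: the plan's either-channel rule.** This dilutes the bias, because some women qualify on the other channel. With X₁ the tested reading, X₂ the other and f the density of X₁:

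expected null change = (1 + r) × SD²(1 − R) × f(c) × P(X₂ > c | X₁ = c) / P(X₁ ≤ c or X₂ ≤ c).

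Every factor is positive when r is zero or above, so the sign does not depend on the other assumed values. For the same case:

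- *r = 0.* Correlation between readings 0.7 × 0.5 = 0.35. SD²(1 − R) = 900 × 0.3 = 270; f(70) = 0.3521/30 = 0.01174; conditional probability 0.636; pass probability 0.617 − 0.141 = 0.476. Result: 270 × 0.01174 × 0.636/0.476 = 4.2 points.
- *r = 0.5.* Correlation 0.7 × 0.5 + 0.3 × 0.5 = 0.5; conditional probability 0.614; pass probability 0.454. Result: 1.5 × 270 × 0.01174 × 0.614/0.454 = 6.4 points.

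**Step 3: the range.** Gains are from the formula. Rejection rates are from simulation of the paired t-test at n = 20 (20,000 trials per cell), with no true effect.

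| Screened mean | Gain, errors independent | Rejection | Gain, errors correlated 0.5 to 0.9 | Rejection |
|---|---|---|---|---|
| 100 | 2.0 to 6.9 | 8–20% | 3.1 to 13.2 | 13–62% |
| 85 | 1.4 to 5.1 | 7–12% | 2.1 to 10.0 | 9–35% |
| 70 | 0.9 to 3.5 | 6–8% | 1.3 to 7.1 | 7–18% |
| 50 | 0.4 to 1.8 | 5–6% | 0.6 to 4.0 | 5–9% |

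Correlated errors are possible because both channels are read in one session. Neither set of columns is a bound.

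**Step 4: more women.** At n = 40 with independent errors, rejection is 12–36%, 9–20%, 7–10% and 5–6% at the four means.

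**Step 5: another baseline.** A same-visit repeat removes a share of the spurious gain equal to the within-session share of the error. For μ = 85, SD 30, R = 0.7, r = 0.5, rejection falls from 0.23 to 0.15, 0.09 or 0.06 when that share is 25%, 50% or 75%. A different-day untreated reading with independent errors gives a null change between −0.14 and +0.09 points and rejection of 0.046 to 0.053.

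**The case against.** The strongest objection is that the size rests wholly on assumption. The trial recruits symptomatic women, so a screened mean below 100 is more plausible, and with independent errors the test is close to its nominal level at means of 70 and 50. This stands. It limits what can be said about size, not about direction, and the documents give nothing that would show the bias to be small.

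Second, the schedule's reference to a reading before each treatment might mean an extra one just before the first treatment. The same line confines the measurement to Visits 2, 4 and 6, those visits already supply a reading before each treatment, and Visit 3 lists none. This is weak.

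Third, a same-visit repeat is a partial cure of unknown strength, and a repeat lowered by fatigue would enlarge the apparent gain. This stands and should be stated with the fix.

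Fourth, the share of women passing the cut-off carries some information. Within the grid above it separates the screened means: about 24–37%, 43–53%, 64–69% and 82–90% at means 100, 85, 70 and 50. A share above about 80% goes with gains of at most about 4 points. But it does not fix the size: at mean 100 and SD 30, shares of 24–27% go with gains from 2.0 to 11.7 points, and SDs outside the grid blur the means as well.

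Fifth, the change from Visit 4 to Visit 6 uses two readings that selected nobody, and its null change is about 0 with rejection of about 5%. That is a useful check, but it measures only the increment after the second treatment.

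**Conclusion.** The concern holds. The entry reading is the baseline for the primary objective, and with no control arm the contraction change at Visits 4 and 6 is biased towards a gain. This requires only that readings contain error, that channel errors are independent or positively correlated, and that the cut-off turns some women away.

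The size cannot be fixed from the documents. Under the assumptions shown it runs from negligible, if most women screened are far below the cut-off or readings are very reliable, to large enough to multiply the false-positive rate several times. The planned comparison therefore cannot by itself measure the effect of Forma V on contraction. This should be fixed; confidence is high for the direction only.

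**What to change.** 1. **Separate the two roles of Visit 2.** Use the first reading for eligibility only, take a repeat in the same visit, and add to the Protocol (Visit 2) and the SAP: *The contraction baseline is the repeat Visit 2 reading; the first Visit 2 reading is used for eligibility only.* State that this removes only the within-session part of the error. If half the error is within session, a screened mean of 85 leaves 0.7 to 2.6 points and about 6–7% rejection with independent channel errors, or 1.1 to 5.0 points and 6–12% with errors correlated 0.5 to 0.9.
2. **Narrow the conclusion.** For contraction, report change from baseline in women selected for low readings, and amend the Efficacy Endpoints wording to match.
3. **Report the numbers** assessed at Visit 2 and failing the cut-off, as context and not as a correction. The Visit 4 to Visit 6 change can be added as a supportive check at no extra measurement cost.

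Optionally, a different-day reading before the first treatment removes the regression component fully if errors are independent between days. Neither baseline removes practice effects or time trends.

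**Cost.** One short repeat per woman and small edits to both documents. Visit 2 carries "Time required: 1.5hrs", while the same listed assessment is given 15 minutes at Visits 4 and 6. Time therefore looks available, though the sponsor should confirm it. Fatigue or practice may shift the repeat, and the reported gain will probably be smaller. The different-day option needs an extra visit to the assessment site, or a therapist at Visit 3.

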#### Exclusion Criteria:

- Internal defibrillator, pacemaker, bladder stimulator or any other implanted electrical device anywhere in the body
- Permanent metal implant in the treatment area
- History of pelvic floor radiation
- Any surgery in the treatment area in the last 3 months
- Current or history of skin cancer, or current condition of any other type of cancer, or pre-malignant moles
- Pregnancy and nursing

- Impaired immune system due to immunosuppressive diseases such as AIDS and HIV, or use of immunosuppressive medications
- Patients with history of diseases stimulated by heat, such as recurrent Herpes Simplex in the treatment area, **may be treated only following a prophylactic regimen.**
- Poorly controlled endocrine disorders, such as diabetes, thyroid dysfunction, polycystic ovary and hormonal virilization
- Any active condition in the treatment area, such as but not limited to open sores, psoriasis, eczema, vitiligo, herpes and rash.
- History of skin disorders, keloids, abnormal wound healing, as well as very dry and fragile skin
- Severe concurrent conditions, such as cardiac disorders, sensory disturbances.
- Use of Isotretinoin (Accutane®) within 6 months prior to treatment.
- Diseases that may be stimulated by light, such as epilepsy, lupus and urticaria.
  
- Any other previous treatments in the vaginal or perineal area, such as CO2 laser or RF performed on the same area.
- Any surgical procedure in the vaginal area within the past 12 months.
- Recent tan from sun, sunbeds or chemicals or planned excessive sun exposure.
- As per the practitioner's discretion, refrain from treating any condition which might make it unsafe for the patient
  
- Participation in this study is not required to receive treatment for pelvic floor relaxation or sexual dysfunction. Patients may receive treatments without participating in the study. Patients may also utilize other methods of treatment including but not limited to Pelvic floor physical therapy, CO2 treatment, or other radiofrequency treatments.

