length and diameter, measurement of the introitus, and length of the labia majora and minora. Measurements will be obtained following POP-Q protocol

- Time required: 15 minutes

**Visit 7:** Midwest Plastic Surgery – Follow-up visit – 8 weeks following second treatment

- Photographs of the treatment area will be taken
- Questionnaires will be completed
- Time required: 45 minutes

- After each treatment and at all visits, adverse events will be recorded.

Duration of each treatment visit is specified.

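### Does the protocol allow participants other pelvic floor treatments during the study, leaving their gains to be credited to the device?

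*Protocol*

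**What the plan says.** The Inclusion Criteria bind anyone who joins. She "will refrain from using any other treatment methods in the treatment areas such surgeries", with CO2 named next, and then "other radiofrequency treatments and fillers injections for the last 12 months and during the entire study period". Physical therapy is not among the named examples. The same section states that "Participants must have an evaluation by the Pelvic Floor Physical Therapists at Antares Institute".

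The last bullet of the Exclusion Criteria has three sentences. The first two are "Participation in this study is not required to receive treatment for pelvic floor relaxation or sexual dysfunction" and "Patients may receive treatments without participating in the study". The third is "Patients may also utilize other methods of treatment including but not limited to Pelvic floor physical therapy, CO2 treatment, or other radiofrequency treatments". An empty heading, *Alternative therapies*, comes straight after it.

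On records, Visit 1 under Study Duration is to "collect all of the required medical information and obtain signed Informed Consent". The visit schedule ends with "After each treatment and at all visits, adverse events will be recorded". No visit description mentions a record of other treatment. Case-report forms and appendices are not among the documents available.

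The primary objective concerns pelvic floor strength, measured by voluntary contraction. The SAP compares before and after with a paired t-test at a two-sided 0.05 level, in everyone with a post-treatment measurement and without adjustment. No control arm is described.

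**The concern.** Taken literally, the third sentence of the bullet gives patients the CO2 and radiofrequency treatments that the Inclusion Criteria take away. It also adds physical therapy, which the Inclusion Criteria do not name. It does not say which patients it means, and it sits in a list that governs enrolment.

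The stake is attribution. Muscle training could raise voluntary contraction directly, and every participant is assessed by pelvic floor physical therapists. If some women began training between the Visit 2 baseline and the readings at Visits 4 and 6, their gain would enter the mean change and count as a device effect. Without a record, nobody could say afterwards how many women were affected.

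**Working it through.** **1. Whom the bullet addresses.**

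- Its first two sentences are about women who get care without joining. The third continues that thought.
- It is not an exclusion criterion in form: it excludes nobody.
- Its content is what the empty *Alternative therapies* heading would be expected to hold. The label and its text may have been separated when the PDF was read; this cannot be proved without the page.
- Read as permission for participants, it would contradict the Inclusion Criteria. It would also sit oddly with an earlier item in its own list, which excludes women previously treated with CO2 laser or radiofrequency in the same area.

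The reading that limits it to non-participants leaves no contradiction on CO2 or radiofrequency.

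**2. Physical therapy.** The Inclusion Criteria bar other treatment methods in general terms and give examples. The bullet itself classes physical therapy as another method of treatment. Taken together, the general restriction plausibly reaches it, but the text does not say so. This is missing detail, not a contradiction.

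**3. Size if some women did co-treat.** Inputs from the documents: n = 20 (the protocol's minimum) and a two-sided paired t-test at 0.05. Assumptions: change scores are normal with SD 1, the device has no effect, and exactly k women gain g = 0.5 or 1 SD from therapy. The documents give neither k nor g.

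False mean change = k × g / 20. For scale, an observed mean change is significant at about 2.093 / √20 = 0.47 SD. Rejection rates are simulated.

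| k | False mean, g = 0.5 to 1 | Two-sided rejection, g = 0.5 to 1 |
|---|---|---|
| 0 | 0 | 5.0% |
| 1 | 0.025 to 0.05 SD | 5.0% to 5.0% |
| 2 | 0.05 to 0.10 SD | 5.3% to 5.9% |
| 4 | 0.10 to 0.20 SD | 6.6% to 10.5% |

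A training gain pushes one way. Counting only results that favour the device (nominal 2.5%), two women give about 4% to 5% and four women about 6% to 10%.

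**4. What a log would let the analyst do.** The main analysis would still use all observed readings. The obvious further step is to drop readings taken after co-treatment began. Suppose the four women with the smallest Visit 4 change start therapy and gain g by Visit 6. Let r be the assumed correlation between the Visit 4 and Visit 6 changes. The 16 women left have a mean Visit 4 change of about 0.33 SD by selection alone, so dropping the four gives a false Visit 6 mean of about 0.33 × r.

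| r | g | All kept: false mean, rejection | Four dropped: false mean, rejection |
|---|---|---|---|
| 0.3 | 0.5 | +0.10, 7.7% | +0.10, 7.0% |
| 0.3 | 1 | +0.20, 13.6% | +0.10, 7.0% |
| 0.5 | 0.5 | +0.10, 8.5% | +0.17, 10.8% |
| 0.5 | 1 | +0.20, 16.1% | +0.17, 10.8% |
| 0.7 | 0.5 | +0.10, 9.6% | +0.23, 17.8% |
| 0.7 | 1 | +0.20, 19.3% | +0.23, 17.8% |

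Dropping gives the lower rejection rate in four of the six cases and the higher in two. It restores 5% in none. In this setting the record does not lead to a corrected analysis.

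**The case for a change.** The best case for a change is that it is cheap and concerns the primary objective. The bullet never limits itself to non-participants, and the Inclusion Criteria also call women entering the study patients, so a site could misapply it. Even if the bullet is set aside, physical therapy is not named among the barred treatments. Medical information taken at screening cannot capture therapy begun later. One question per visit would give a count that is hard to recover afterwards. Heavy uptake would also matter: with 10 of 20 women gaining 0.5 to 1 SD, a no-effect device would test significant about 17% to 47% of the time.

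Part of this stands. The wording is loose, the status of physical therapy is left to inference, and a count would help in describing the results. The rest does not carry. Heavy uptake needs half the participants to act against the general restriction on its natural reading, and no passage says that any participant trains or is offered therapy. The assessing therapists are described as evaluating, not treating. A co-treatment record may also exist in the case-report forms, which are not available here.

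Nor would the count answer the question of cause. A paired before-after comparison cannot tell training from device with or without a log. Other non-device gains would remain as well, such as regression to the mean after selecting women at least 30% below average.

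**Conclusion.** No change to the statistical plan follows. The apparent permission to co-treat depends on the less likely reading of a bullet that seems to describe alternatives to taking part. Participants are already under a general restriction for the whole study. What is left is a clerical ambiguity and a detail of data collection that a trial team would ordinarily settle in its forms.

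If the protocol text is edited for other reasons, the two sections should be reconciled on whom the bullet addresses and on whether the restriction takes in physical therapy. That rule is for the investigators to set.

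The effect is negligible with one or two co-treated women of 20 (two-sided error about 5.0% to 5.9%) and small to moderate with four (about 6.6% to 10.5%). These figures rest on assumed uptake, an assumed gain of 0.5 to 1 SD, normal change scores and no device effect. The conclusion would weaken if the bullet were shown to apply to participants or if many women trained during the study; the documents give no sign of either.
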